#### PROTOCOL/AMENDMENT NO.: 002-07

- 4. Grade 2 (per current version of NCI CTCAE) or worse conduction defect (eg, right or left bundle branch block)
- 5. Major surgical procedures or locoregional therapy within 4 weeks of the first dose of miransertib
- 6. Any experimental systemic therapy for the purposes of treating PROS or PS (eg, sirolimus, everolimus, high dose steroids) within 2 weeks of the first dose of miransertib
- 7. Intolerance of or severe toxicity attributed to AKT inhibitors (eg, miransertib, uprosertib, afuresertib, ipatasertib)
- 8. Concurrent severe uncontrolled illness not related to PROS or PS, including:
  - Ongoing or active infection
  - Known HIV infection
  - Malabsorption syndrome
  - Psychiatric illness/substance abuse/social situation that would limit compliance with study requirements
- 9. Pregnant or breastfeeding
- 10. Inability to comply with study evaluations or to follow drug administration guidelines

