#### 4 STUDY VISITS

Before the start of any study required procedures, the investigator or designee must obtain a signed written ICF and, when applicable, signed assent for the study from each prospective participant or his/her parent or legal guardian.

For Part A, all ongoing participants will continue treatment and will follow the Schedule of Events in Annex 1.

For Part B Cohorts 1, 2 and 3, study visits will consist of a Screening Visit, (during which the participant's eligibility for the study and baseline disease state will be evaluated), 2 visits during the first and fourth cycles, one visit per cycle for Cycles 2 and 3, and 5, then once every 2 cycles for Visits 7, 9, 11, and 13, and then one visit per every 3 cycles until EOT, during which the participant's clinical status will be evaluated, and a 30-Day Safety Follow-up (Table 3).

For participants enrolled in Cohort 4, study visits will consist of a Screening Visit, (during which the participant's eligibility for the study and baseline disease state will be evaluated), Cycle 1 Day 1 visit and then one visit per every 3 cycles (eg, Cycle 4 Day 1, Cycle 7 Day 1,

Cycle 10 Day 1, Cycle 13 Day 1, etc.) until EOT, during which the participant's clinical status will be evaluated, and a 30-Day Safety Follow-up (Table 4).

After the Screening Visit and a determination by the investigator and with Sponsor approval that the participant meets all inclusion criteria and none of the exclusion criteria, the participant will be considered entered into the study.

Participants enrolled in Part B, Cohorts 1 and 2, must also meet eligibility requirements according to applicable central imaging criteria.

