# 5.2 12-Lead Electrocardiogram

A 12-lead ECG will be conducted at specific timepoints (see Table 3 and Table 4). Additional ECGs may be conducted if clinically indicated or required per standard of care (triplicate if possible). The ECG parameters will be captured in the EDC database and copies of ECG tracings will be collected and forwarded for future analyses by the Sponsor or its designee.

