## 5.8 Schedule of Events

## 5.8.1 Cohorts 1, 2, and 3

Table 3 is intended as a list of visits and associated assessments. Please refer to relevant protocol sections for detailed information.

Table 3 Schedule of Events Part B Cohorts 1, 2 and 3

Phase	Screening	Screening Treatment (Year 1) 1						Follow	Follow-Up	
Tests & Procedures / Visit Name	Screening	C1D1	C1D15 C4D15	C2, C3, C5, C9, C11,	C4D1	C7, C13	C16, C19, C22, C25, C28, C31, C34, C37, C40, C43, C46	EOT (C48)	30-day Safety Follow-up	
Window (days)	-14 to 0	-1 to 0	± 3	± 5		± 5	± 5	Within 7 days	30+ Days	
Written informed consent	X									
Medical history	X									
Physical examination	X	X	X	X	X	X	X	X	X	
Vital signs	X	X	X	X	X	X	X	X	X	
Calculate BSA / dose		X		X	X	X	X			
Dose increase to 25 mg/m 					X					
12-lead ECG		X	X		X			X	X	
Fasting clinical blood tests	X			X	X	X	X	X	X	
Insulin/glucose blood tests	X					X	X (C19, C25, C37)	X		
Urinalysis	X			X	X	X	X	X	X	
Serum pregnancy test (if applicable)	X							X	X	
Dispense study medication 		X		X	X	X	X			
Collect and count returned miransertib capsules				X	X	X	X	X		
Concomitant medications	X	X	X	X	X	X	X	X	X	
Adverse events		X	X	X	X	X	X	X	X	

BSA=body surface area; C=cycle; D=day; ECG=electrocardiogram; EOT=end of treatment.

The following CXDX visit assessments may be performed within a 24-hour window of dosing (Physical Examination, ECG)

Dispense monthly allotments at C1, C2, C3, C4; 2-month allotments at C5, C7, C9, C11; 3-month allotments at C13, C16, C19, C22, C25, C28, C31, C34, C37, C40, C43; 2-month allotment at C46

## **5.8.2** Cohort 4

Table 4 is intended as a list of visits and associated assessments. Please refer to relevant protocol sections for detailed information.

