**Table 4 Schedule of Events Part B Cohort 4** 

Phase	Screening	1	Гreatment (	(year 1)	Treatment (years 2	Follow-Up	
Tests & Procedures / Visit Name	Screening	C1	C4	C7, C10, C13	C16, C19, C22, C25, C28, C31, C34, C37, C40, C43, C46	EOT (C48)	30-day Safety Follow-up
Window (days)	-14 to 0	-1 to 0	± 5	± 5	± 5	Within 7 days	30+ Days
Written informed consent	X						
Medical history	X						
Physical examination	X	X	X	X	X	X	X
Vital Signs	X	X	X	X	X	X	X
Calculate BSA / dose		X	X	X	X		
12-Lead ECG		X	X			X	X
Fasting clinical blood tests	X		X	X	X	X	X
Insulin/glucose blood tests	X			X	X (C19, C25, C37)	X	
Urinalysis	X		X	X	X	X	X
Serum pregnancy test (if applicable)	X					X	X
Tissue biopsy	X						
Blood for CYP2D6		X					
Lesion measurement by imaging (e.g. DXA)	X						
Dispense miransertib 		X	X	X	X		
Collect and count returned miransertib capsules			X	X	X	X	
Concomitant medications	X	X	X	X	X	X	X
Adverse events		X	X	X	X	X	X

BSA=body surface area; C=cycle; DXA=dual-energy X-ray absorptiometry ECG=electrocardiogram; EOT=end of treatment.

Dispense 3-month allotments from C1 through C43; dispense 2-month allotment at C46.

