## **Schedule of Events Part A**

This table is intended as a cumulative list of visits and associated assessments.

Phase	Screening		Treat	ment (Year 1)		Treatment (Y	ears 2-4)		Follow-U	р
Tests & Procedures / Visit Name	Screening	C1D1	C1D15 C4D15 C7D15	C2, C3, C5, C6, C8, C9, C11, C12 Day 1	C4D1 C7D1 C10D1 C13D1	C16, C19, C22, C28, C31, C34, C40, C43, C46 Day 1	C25D1 C37D1	ЕОТ	30-day Safety Follow-up	3 Month Follow-up
Window (days)	-14 to 0	-1 to 0	± 3	± 5	± 5	± 5	± 5	Within 7 days	30+ days	±14 days
Written informed consent	X									
Medical history	X									
Physical examination	X	X	X	X	X	X	X	X		X
Vital Signs	X	X	X	X	X	X	X	X		X
Calculate BSA / dose		X		X	X	X	X			
12-Lead ECG	X			X	X	X	X	X		X
Fasting clinical blood tests	X			X	X	Х	X	X		X
Insulin/glucose blood tests			X							
Urinalysis	X				X	X	X	X		X
Serum pregnancy test (if applicable)	X							X		X
Disease Measurement	X				X					
Dispense miransertib		X		X	X	X	X			
Collect and count returned miransertib				X	X	X	X	X		

Phase	Screening		Treati	nent (Year 1)		Treatment (Y	ears 2-4)		Follow-U	p
Tests & Procedures / Visit Name	Screening	C1D1	C1D15 C4D15 C7D15	C2, C3, C5, C6, C8, C9, C11, C12 Day 1	C4D1 C7D1 C10D1 C13D1	C16, C19, C22, C28, C31, C34, C40, C43, C46 Day 1	C25D1 C37D1	ЕОТ	30-day Safety Follow-up	3 Month Follow-up
Window (days)	-14 to 0	-1 to 0	± 3	± 5	± 5	± 5	± 5	Within 7 days	30+ days	±14 days
Concomitant medications	X	X	X	X	X	X	X	X	X	X
Adverse events		X	X	X	X	X	X	X	X	X

<sup>1 C4D15 visit will only occur if the dose (mg/m²) increases at Cycle 4. C7D15 visit will only occur if the dose (mg/m²) increases at Cycle 7.

<sup>2 CYP2D6 at C1D15 ONLY. If not collected at C1D15 for previously enrolled participants, it will be collected at the next Cycle visit after reconsenting under the amended protocol.

<sup>3 ECG and PK are tested at C2D1 for all participants and at C5D1 and C8D1 only if the dose was increased at Cycle 4 and Cycle 7, respectively.

<sup>4 Blood for PK ONLY collected at C4D1 and C7D1.

<sup>5 Disease Measurement by US, photography and/or video recording only on C4D1 if no dose increase.

<sup>6 Dispense 3-cycle supply of drug at C13D1 if participant is continuing beyond the first 12 cycles of therapy.

<sup>7 ECGs will only be performed if clinically indicated or if required per standard of care.

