
 
Physical examination, including skin
 
Vital signs (height, weight, temperature, blood pressure, respiration rate, and heart rate)
 
Calculate BSA using the DuBois formula
 
12-lead ECG, predose (ONLY Cycle 2 Day 1)
 
Fasting Clinical Blood Tests
 
Where relevant, additional functional test(s) to evaluate individual participant disease status – frequency as per standard of care
 
Dispense miransertib
 
Collect and count returned miransertib
 
Record concomitant medication
 
Assess AEs
 
	
 
Physical examination, including skin
 
Vital signs (height, weight, temperature, blood pressure, respiration rate, and heart rate)
 
Calculate BSA using the DuBois formula
 
12-lead ECG, predose
 
Fasting Clinical Blood Tests Urinalysis
 
Fibrinogen and D-dimers
 
Dispense miransertib
 
Collect and count returned miransertib
 
Record concomitant medication
 
Assess AEs
 
	
 
Physical examination, including skin
 
Vital signs (height, weight, temperature, blood pressure, respiration rate, and heart rate)
 
Calculate BSA using the DuBois formula
 
12-lead ECG, predose
 
Fasting Clinical Blood Tests Urinalysis
 
Optional lesion biopsy (ONLY Cycle 13)
 
Fibrinogen and D-dimers
 
Where relevant, additional functional test(s) to evaluate individual participant disease status – frequency as per standard of care
 
Dispense miransertib (dispense 3-cycle supply at C13 if participant is continuing beyond first 12 cycles of treatment)
 
Collect and count returned miransertib
 
Record concomitant medication
 
Assess AEs
 

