## **Study Visits – After 12 Cycles of Treatment**

Cycles* 16, 19, 22, 28, 31, 34, 40, 43 and 46 - Day 1 (± 5 days)	Cycles* 25 and 37 - Day 1 (± 5 days)

 
Physical examination, including skin
 
Vital signs (height, weight, temperature, blood pressure, respiration rate, and heart rate)
 
Calculate BSA using the DuBois formula
 
12-lead ECG, predose, if clinically indicated or required per standard of care
 
Fasting Clinical Blood Tests Urinalysis
 
Urinalysis
 
Dispense miransertib
 
Collect and count returned miransertib
 
Record concomitant medication
 
	
 
Physical examination, including skin
 
Vital signs (height, weight, temperature, blood pressure, respiration rate, and heart rate)
 
Calculate BSA using the DuBois formula
 
12-lead ECG, predose
 
Fasting Clinical Blood Tests
 
Urinalysis
 
Dispense miransertib
 
Collect and count returned miransertib
 
Record concomitant medication
 

• Assess AEs	Assess AEs

\*After the initial 12 months of treatment, the participant may continue receiving treatment and will be seen at the study site once every 3 months per the schedule outlined above.

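### Part B schedules no Screening ECG, and nothing requires the first scheduled ECG (C1D1 or C1) to be done and read before the first dose

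*Protocol*

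**What the plan says.** Protocol Section 3.2, exclusion 4, rules out a participant with a Grade 2 "or worse conduction defect (eg, right or left bundle branch block"). Section 4 ties entry into the study to the eligibility decision: "After the Screening Visit and a determination by the investigator and with Sponsor approval that the participant meets all inclusion criteria". The same sentence also requires that no exclusion applies.

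For the ECG itself, Section 5.2 refers to the schedules: "A 12-lead ECG will be conducted at specific timepoints (see Table 3 and Table 4"). It also allows extra ECGs if clinically indicated or per standard of care. In Table 3 (Cohorts 1, 2 and 3) the ECG row is blank at Screening and first marked at C1D1. In Table 4 (Cohort 4) it is blank at Screening and first marked at C1. Both first ECGs have a visit window of -1 to 0 days.

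The only timing note for Part B ECGs is under Table 3: "The following CXDX visit assessments may be performed within a 24-hour window of dosing (Physical Examination, ECG"). Table 4 has none.

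SAP 4.2.2 takes as baseline the last non-missing value, scheduled or not, before the first dose of miransertib. SAP 4.19 tabulates observed values and changes from baseline for PR, RR, QRS, QT and QTc, and summarises the overall interpretation at each visit.

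**The concern.** A bundle branch block that nobody knows about is found by ECG, not by history or examination. Where an exclusion depends on such a finding, one expects an ECG at Screening, or else a rule that the Day 1 ECG is done and read before dosing. Part B has neither.

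Two things are at stake. The first is safety: a participant, possibly a young child, could receive the drug before the cardiac exclusion has been checked by any ECG. The second is analysis: if the C1D1 or C1 ECG is recorded after the dose, it cannot be the SAP baseline, and the participant drops out of the ECG change summaries unless some other pre-dose ECG exists.

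**Working it through.** The plan gives no figure to reproduce here. The check is a reading of the schedules against the rules that depend on them.

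**1. Scheduled ECGs**

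| Schedule | At Screening | First ECG | All ECG timepoints |
|---|---|---|---|
| Table 3, Cohorts 1 to 3 | 0 | C1D1 | C1D1, C1D15, C4D1, C4D15, EOT, 30-day follow-up (6) |
| Table 4, Cohort 4 | 0 | C1 | C1, C4, EOT, 30-day follow-up (4) |
| Annex 1, Part A | 1 | Screening | not needed for this point |

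In both Part B tables, blood tests, urinalysis and the pregnancy test are marked at Screening. The ECG row is the one left blank.

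**2. What Part A did.** Part A has the same conduction-defect exclusion (Annex 1, exclusion 2). It marks an ECG at Screening in both the schedule and the Screening visit list. Its Cycle 1 Day 1 list also has the first dose given once the assessments above it are finished, post-dose blood draws aside. The current Part B text has no equivalent sentence.

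**3. Must the Part B C1D1/C1 ECG precede the dose?**

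- *Visit window.* Day -1 is before dosing. Day 0 is the dosing day and includes the hours after the dose. The window permits a pre-dose ECG but does not require one.
- *Table 3 footnote.* It gives 24 hours around dosing without saying before or after, and does not set C1D1 apart.
- *Laboratory rule.* Section 5.3 also gives a 24-hour allowance but excepts C1D1. The protocol made that exception for laboratory tests and not for the ECG.
- *Table 4.* Only the visit window applies.
- *Section 2.2.* For Cohorts 1 to 3 it calls for safety assessments at baseline. Its examples do not include the ECG, and it leaves the detail to Table 3.

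No Part B text requires the ECG to be done before the first dose, or to be read before it.

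**4. Consequence for the SAP.** A C1D1/C1 ECG taken after the dose fails the SAP 4.2.2 definition. With nothing scheduled at Screening, the baseline is then missing unless an unscheduled pre-dose ECG was recorded. Changes from baseline in the five intervals are lost for that participant. Observed values and the normal/abnormal interpretation are still reported.

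**5. Cohort 4.** Under Section 6.3, participants already receiving miransertib at entry continue their dose. Their C1 ECG is on treatment even if taken before the first study dose, so it is not a drug-free baseline. The documents do not say how many of the approximately 10 planned Cohort 4 participants (SAP 2.3) are in this position.

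**The case against.** The strongest reply is that the Part B ECG is plainly meant to be a pre-dose one. The C1D1 window allows deviation only to the earlier side, and Section 2.2 speaks of baseline assessments. Section 3 requires that no exclusion be met, so a site that doses without resolving exclusion 4 is not following the protocol as a whole. This has weight: most sites will probably do the ECG first. It does not remove the gap, because the one explicit timing rule, the Table 3 footnote, permits the opposite order.

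A reader might go further and infer that no scheduled Part B test can find a conduction defect before the participant counts as entered. The documents do not support that. The Screening window (-14 to 0 days) overlaps the C1D1 window (-1 to 0 days), and Section 4 does not date the eligibility decision before the C1D1 ECG. Other eligibility items also stay open until dosing: age is judged at C1D1 (Section 3.1.1), and mutation status must be confirmed before dosing (Section 5.1). A Day -1 or pre-dose Day 0 ECG can inform eligibility; it is just not required to.

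A reader might also set the Part A visit lists, with entries such as "12-lead ECG, predose (ONLY Cycle 2 Day 1") and "12-lead ECG, predose, if clinically indicated or required per standard of care", against Part B and conclude that the protocol deliberately omitted the label. That comparison is not like for like. Those labels are in visit lists for Cycle 2 and later, and Part A has no ECG at Cycle 1 Day 1. The Part A schedule table has no such label in its ECG row either. The summary of changes records that Amendment 7 deleted the appendix of Part B study visits, whose content is not available.

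Finally, the remedy adds no Screening ECG. That is consistent with the point: a Screening ECG is unnecessary if the scheduled C1D1/C1 ECG is done and read in time.

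**Conclusion.** The point holds as a gap in a stated requirement, not as evidence that anyone was harmed or wrongly enrolled. Part B schedules no ECG at Screening, and its rules allow the first dose before the C1D1/C1 ECG is done or read. A participant dosed in that order would lack ECG change-from-baseline values unless an unscheduled pre-dose ECG exists.

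The number of participants affected is not given and may be zero. Amendment 7 completes final enrolment (Section 2.1), so few first doses may remain, and participants enrolled before it may have followed a schedule not shown in the current text. A share of a cohort's ECG data cannot be calculated without assuming a number of missing baselines, so none is offered. The exposed summaries are descriptive; the adverse event endpoint is not affected.

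The conclusion assumes that the ECG rows of Tables 3 and 4 are complete as extracted; they line up with their column headers. The change is worth making because it is cheap and protects both the exclusion check and the baseline.

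**What to change.** In the protocol:

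- Label the C1D1 ECG in Table 3 and the C1 ECG in Table 4 as predose.
- Limit the Table 3 footnote at C1D1 to the 24 hours before the first dose.
- State in Section 4 or 5.2 that this ECG must be read against exclusion 4 before the first study dose.

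Optionally, add to SAP 4.19 a count by cohort of participants with an ECG before the first dose. Show separately the Cohort 4 participants already receiving miransertib at entry, and note that their value is not a drug-free baseline. This count stays useful after enrolment has ended.

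The cost is one label in two tables, one phrase in a footnote, one sentence and, if adopted, one SAP count. No procedure is added. The downside is that Day 1 dosing may wait briefly for the ECG to be read.

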**Table 4 Schedule of Events Part B Cohort 4** 

Phase	Screening	1	Гreatment (	(year 1)	Treatment (years 2	Follow-Up	
Tests & Procedures / Visit Name	Screening	C1	C4	C7, C10, C13	C16, C19, C22, C25, C28, C31, C34, C37, C40, C43, C46	EOT (C48)	30-day Safety Follow-up
Window (days)	-14 to 0	-1 to 0	± 5	± 5	± 5	Within 7 days	30+ Days
Written informed consent	X						
Medical history	X						
Physical examination	X	X	X	X	X	X	X
Vital Signs	X	X	X	X	X	X	X
Calculate BSA / dose		X	X	X	X		
12-Lead ECG		X	X			X	X
Fasting clinical blood tests	X		X	X	X	X	X
Insulin/glucose blood tests	X			X	X (C19, C25, C37)	X	
Urinalysis	X		X	X	X	X	X
Serum pregnancy test (if applicable)	X					X	X
Tissue biopsy	X						
Blood for CYP2D6		X					
Lesion measurement by imaging (e.g. DXA)	X						
Dispense miransertib 		X	X	X	X		
Collect and count returned miransertib capsules			X	X	X	X	
Concomitant medications	X	X	X	X	X	X	X
Adverse events		X	X	X	X	X	X

BSA=body surface area; C=cycle; DXA=dual-energy X-ray absorptiometry ECG=electrocardiogram; EOT=end of treatment.

Dispense 3-month allotments from C1 through C43; dispense 2-month allotment at C46.

#### 6 TREATMENT

#### 6.1 Miransertib

Miransertib capsules will be supplied to the pharmacy at the clinical site in bottles containing 30 capsules each. Study medication will be labeled as an investigational agent, limited by federal and other applicable laws, as required. The appropriate number of bottles will be dispensed to the participant to ensure that they have sufficient drug at the prescribed dose level until their next drug dispensing visit. Miransertib should be stored according to the instructions provided on the bottle label.

## 6.2 Miransertib Accountability

The Sponsor will provide all study medication required for completion of this study. The recipient will acknowledge receipt of the drug indicating shipment content and condition. Damaged supplies will be replaced. Until dispensed to the participants, the study medication will be stored in a secure locked area, accessible to authorized personnel only. Drug accountability records will be maintained. The clinical site's pharmacy records should record quantities of study medication received and quantities dispensed to participants, including the lot number, date received and dispensed, participant identifier number, participant initials (when applicable), protocol number, dose, quantity returned, balance remaining, and the initials of the person dispensing the drug. Accurate records of all study medication dispensed from and returned to the clinical site are to be maintained. The clinical site must supply a copy of their drug destruction policy to the Sponsor before authorization for destruction will be granted. Product accountability will be monitored throughout the study. On completion or termination of the study, and after inventory by the Sponsor's monitor or designee, all unopened drug is to be returned to the Sponsor or designee in the original containers.

#### 6.3 Miransertib Administration

In Part A, the first 6 participants (all with PROS) were enrolled in the dose escalation cohort and treated at 15 mg/m² qd for 3 cycles, with a cycle defined as 28 days. They were allowed to have 2 dose escalations (25 mg/m², 35 mg/m² qd). Only the first participant had the dose increased to 35 mg/m². Subsequently, based on nonclinical and clinical data from the NHGRI, and data from the 6 participants in this study, 15 mg/m² qd for at least 3 cycles with an option to dose increase to 25 mg/m² was determined to be safe. All subsequently enrolled participants received miransertib at 15 mg/m², with a dose increase to 25 mg/m² permitted after either 3 or 6 cycles of therapy.

For Part B (Cohorts 1, 2, and 3), participants will receive miransertib at the starting dose of 15 mg/m^2 qd for the first 3 cycles, (a cycle of therapy is 28 days), and then the dose will be increased to 25 mg/m^2 qd, provided no clinically significant drug-related toxicity is observed.

Participants in Cohort 4 receiving miransertib at the time of enrollment under Compassionate Use/Expanded Access will continue with their current dose, but their dose should not exceed 25 mg/m^2. Participants who previously received miransertib but were not on the study medication at the time of enrollment, will receive miransertib at the starting dose of

15 mg/m^2 qd for the first 3 cycles with a potential dose increase to 25 mg/m^2 qd, provided no clinically significant drug-related toxicity is observed. Actual dose will be calculated using BSA, per the DuBois formula.

Miransertib will be supplied as 5 and 10-mg capsules, which should be taken either 1 hour before or 2 hours after a meal. Capsules should be swallowed whole. The preferred beverage for administration is water. However, in cases where there is a medical problem affecting the participant's ability to swallow (eg, the participant has an enlarged tongue), the capsules can be opened, and the powder contents sprinkled onto a small amount of sweetened semiliquid food (eg, apple sauce, chocolate syrup, or ice cream) and administered in its entirety to the participant. The same type of semiliquid food should be used, if possible, for the duration of the study. Refer to the Pharmacy Manual for specific instructions on opening the capsules. To maximize safety and avoid unnecessary exposure to the drug by caregivers, it is recommended that gloves and a facemask be worn by the caregiver when handling opened capsules and that the gloves and facemask are discarded along with the empty capsule shells after use. Pregnant women should not open the capsules.

Miransertib will be administered once daily. Dose will be calculated based on BSA, and actual dose level will be rounded to the nearest 5 mg using a dosing nomogram (Appendix 2). Miransertib will be capped at a BSA >1.77 m^2. During site visits, miransertib dosing will be adjusted for changes in BSA according to the dosing nomogram.

Participants and/or their guardians must use the diary card provided to keep a record of daily intake of each dose of miransertib and the method of administration (capsules swallowed whole or opened and swallowed with semiliquid).

